##### **9.1.4.2 Postprandial glucose and mixed meal tolerance test**

Patients will undergo assessment of PPG at Visit 3 (Baseline) and Visit 9 (Week 26) via a mixed meal tolerance test (MMTT) to allow estimation of change from Baseline to Week 26 in 2-hour PPG following a MM. Full details of the MMTT procedure at Baseline and Week 26 are presented in [Appendix B](#).

At Visit 3 (Baseline) and Visit 9 (Week 26), PPG values will be assessed by MMTT at baseline (fasting) and 2 hours after consuming a standard mixed liquid breakfast meal.

The first dose of double-blind IMP on Day 1 (Baseline; Visit 3) will be given **after** completion of the 2-hour PPG collection. For the Week 26 standardized MM, the patient should take the dose of

double-blind IMP immediately **after** the fasting blood samples are obtained, and approximately 30 minutes **before** ingestion of the standardized MM begins.

Plasma concentration samples at Week 26 should be taken at the same times as the fasting blood sample and the 2-hour central laboratory plasma PPG collection (see [Section 9.3.1.1](#)).

The composition and the quantity of the standard mixed liquid breakfast meal must be identical throughout the study; see [Appendix B](#) for further details.

All patients should undergo the standardized MMTT at Visit 9 (Week 26), including those rescued before Visit 9.

In case of permanent discontinuation of the treatment with IMP before Visit 9 (Week 26), every effort will be made to have the patient return to the site at the time of their Visit 9 (Week 26); however the MMTT should not be performed at this or any other visit following a Premature EOT visit.

On the days of the MMTT, patients will come to the investigational site in the morning, in fasting conditions for at least 8 hours and must not eat any food or drink, except water, before the scheduled standardized meal test.

The exact times of the IMP administration, standard mixed liquid breakfast meal intake, and the blood draws are to be documented.

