### **10.3.3 List of criteria for permanent treatment discontinuation**

The patients may withdraw from treatment with the IMP at any time for any reason or this may be the Investigator's decision. Patients should discuss stopping study medication with the site before doing so in order that questions can be addressed, glycemic therapy adjusted, and a follow-up assessment arranged. All efforts should be made to document the reasons for treatment discontinuation and this should be documented in the e-CRF.

The following reasons lead to permanent discontinuation:

- At the patient's own request (ie, withdrawal of consent for treatment)
- If, in the Investigator's opinion, continuation with the administration of the study treatment would be detrimental to the patient's well-being
- Inter-current condition that requires permanent discontinuation of the study treatment as long as the abnormality persists and if the causal relationship of the concerned event and the IMP is possible (according to the Investigator's best medical judgment)
- Pregnancy (in female patients)
- Specific request of the Sponsor

Any abnormal laboratory value will be rechecked immediately for confirmation before making a decision of permanent discontinuation of the IMP for the concerned patient.

For patients who prematurely discontinue the IMP, the assessments planned at EOT visit ([Section 10.1.2.1.2](#)) will be performed at the Premature EOT Visit, scheduled preferably prior to treatment discontinuation or as soon as possible after time of discontinuation the latest at the next on-site visit). Reason for IMP discontinuation will be clearly specified. This Premature EOT assessment may occur at a regularly scheduled visit or at an unscheduled visit.

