## **Appendix B Two-hour standardized mixed meal**

A 2-hour PPG will be obtained after a standardized MM in all patients at Baseline (Day 1, Visit 3) and at Week 26 (Visit 9), or earlier if the patient terminates study participation before Week 26. Any patient who requires the addition of rescue medication should undergo the second standardized MMTT at Visit 9 (Week 26).

The standardized MM must not be done while patients are temporarily off IMP; the Medical Monitor will address any episodes on a case-by-case basis and the standardized MM will be rescheduled when the patient can resume IMP, if applicable.

The first dose of double-blind IMP on Day 1 (Visit 3) will be given AFTER completion of the 2-hour PPG collection. For the Week 26 standardized MM, the patient should take the dose of double-blind IMP immediately after the fasting blood samples are obtained, and approximately 30 minutes **before** ingestion of the standardized MM begins.

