1.3 DETERMINATION OF SAMPLE SIZE

In the original version of the protocol, the sample size/power calculations were performed based on the primary variable, change in HbA1c from baseline to Week 26. Assuming a common standard deviation (SD) of 1.2% and using a 2-sided test at a 0.05 α -level, 120 patients per arm would have 95% power to detect a treatment difference of 0.6% in mean HbA1c change from Baseline to Week 26 between sotagliflozin 400 mg and placebo.

In Amendment 1, the sample size/power has been recalculated to account for the addition of the sotagliflozin 200 mg treatment group after enrollment had commenced. Assuming a common standard deviation (SD) of 1.2% and using a 2-sided test at a 0.05 α -level, 100 patients per arm will have

- 94% power to detect a treatment difference of 0.6% in mean HbA1c change from Baseline to Week 26 between sotagliflozin 400 mg and placebo, and
- 84% power to detect a treatment difference of 0.5% in mean HbA1c change from Baseline to Week 26 between sotagliflozin 200 mg and placebo.

As a result, the total number of patients will include:

- 76 patients randomized (1;1) under the original protocol, balanced between placebo and sotagliflozin 400 mg, and
- Approximately 300 patients to be randomized (1:1:1) under Amendment 1, balanced among placebo, sotagliflozin 200 mg and sotagliflozin 400 mg doses.

Statistical Analysis Plan

[figure not shown]
Version: 3

Lexicon Pharmaceuticals Protocol No. EFC14833

Date of Issue: 21-Nov-2019

Covance Study ID: 000000150524

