2.4.4.1 Analysis of primary efficacy endpoint(s)

The statistical tests will be two-sided tests at a nominal 5% significance level.

Primary analysis

The primary efficacy endpoint of change in HbA1c from baseline to Week 26 will be analyzed by an Analysis of Covariance (ANCOVA) model using HbA1c values measured at baseline and Week 26 (observed or imputed). The missing data at endpoint will be imputed by multiple imputation (MI) methods in 2 parts as detailed below. To be concise, the following texts related to imputation are generalized to accommodate primary as well as continuous secondary efficacy endpoints.

Statistical Analysis Plan

Version: 3

Lexicon Pharmaceuticals Protocol No. EFC14833

Date of Issue: 21-Nov-2019

Covance Study ID: 000000150524

Missing endpoint data at Week 26 (or Week 12 for SBP) visit will be imputed using a model built separately in each treatment group and estimated from the patients in the same treatment group who prematurely discontinue the IMP before the Week 26 (or Week 12 for SBP) visit but have the measurement for the endpoint (ie, retrieved dropouts). The imputation model will include the randomization strata and the corresponding baseline value. In cases of non-convergence during the imputations, the offending stratum will be identified and then will be dropped from the model. Considering that the number of retrieved dropout patients in each treatment group is expected to be small, a simple imputation model based on regression will be used with baseline measurement included as the predictor. This will serve as the primary method of imputation for missing data should sampling criteria be satisfied (see below).

An alternative (back-up) imputation method will be used if the number of patients who prematurely discontinue the IMP before the Week 26 (or Week 12 for SBP) visit but have the measurement for the endpoint is < 5 in any treatment groups (ie, an insufficient number of retrieved dropouts to support the imputation method described above). This criterion will be assessed for each primary or continuous secondary efficacy endpoint.

In the back-up imputation method, missing post-baseline endpoint values at Week 26 (or Week 12 for SBP) will be imputed by the washout Multiple Imputation (MI) method under the missing not at random (MNAR) framework.

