2.5.4 Windows for time points / Measurements for analyses

The following steps will decide how the scheduled and/or unscheduled visits will be used in the analyses on efficacy variables and the by-visit summaries for safety variables (clinical laboratory data in [Section 2.1.4.4](#) and vital signs in [Section 2.1.4.5](#)).

Step 1 A scheduled measurement will be used if it is available; otherwise, an unscheduled measurement (including the end of treatment/study visit for those prematurely discontinued) will be used if it happens to be on the same date as the date of the scheduled visit.

Step 2 After Step 1, if there are still no measurement for a given parameter at a scheduled visit, the analysis window below ([Table 4](#)) will be applied to re-allocate a post-baseline unscheduled measurement to a scheduled measurement.

Table 4 - Analyses window definition

Scheduled visit post baseline	Targeted study day	Analysis window in study days
Week 1 (Visit 4)	7	2 to 17
Week 4 (Visit 5)	28	18 to 41
Week 8 (Visit 6)	56	42 to 69
Week 12 (Visit 7)	84	70 to 104
Week 18 (Visit 8)	126	105 to 153

Statistical Analysis Plan

Version: 3

Lexicon Pharmaceuticals Protocol No. EFC14833

Date of Issue: 21-Nov-2019

Covance Study ID: 000000150524

Scheduled visit post baseline	Targeted study day	Analysis window in study days
Week 26 (Visit 9)	182	≥154

Study days are calculated from the day of first administration of double-blind IMP; the day of first administration of IMP (or the day of randomization if not exposed) is Day 1.

After applying the above time windows, if multiple assessments are associated to the same time point, the closest from the targeted study day will be used. In case of equality, the last measurement will be used. Re-allocated scheduled visits (ie, visit numbers) should be sequential if ordered by the date of measurement.

After Step 2, if there are still no measurement for a given parameter at a scheduled visit, data is considered missing for efficacy analyses, where multiple imputation would be applied as appropriately as described in [Section 2.4.4](#).

Reference day

The reference day for the calculation of extent of exposure, time to onset, and relative days will be the day of the first administration of double-blind IMP or the day of randomization if not exposed to double-blind IMP, denoted as Day 1.

Baseline definition for efficacy/safety data

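### The SAP's retrieved-dropout definition does not require the endpoint value to follow the last dose, so late on-drug Premature EOT values can act as donors; for 2-hour PPG no other protocol-compliant donors exist

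*SAP*

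**What the plan says.** **Donor definition.** SAP 2.4.4.1 estimates the imputation model, arm by arm, from donor patients, defined as those that "prematurely discontinue the IMP before the Week 26 (or Week 12 for SBP) visit but have the measurement for the endpoint (ie, retrieved dropouts"). If any arm has fewer than 5 such patients, that endpoint goes to washout multiple imputation (MI). There, missing sotagliflozin values are drawn from a model fitted to placebo completers. The criterion is checked endpoint by endpoint.

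**What counts as having the measurement.** SAP 2.4.4 leaves this to the windowing steps in 2.5.4. A scheduled value comes first. Failing that, "an unscheduled measurement (including the end of treatment/study visit for those prematurely discontinued) will be used" if its date matches the scheduled visit. Failing that, a window "will be applied to re-allocate a post-baseline unscheduled measurement to a scheduled measurement". The Week 26 window is Day 154 onward (target Day 182); the Week 12 window is Days 70 to 104 (target Day 84).

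**When the Premature EOT visit happens.** Protocol 10.3.3 says the EOT assessments "will be performed at the Premature EOT Visit, scheduled preferably prior to treatment discontinuation", or otherwise as soon as possible afterwards, at the latest at the next on-site visit.

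**The meal test.** For patients who stop IMP early, Protocol 9.1.4.2 asks for a return at Week 26, "however the MMTT should not be performed at this or any other visit following a Premature EOT visit". Protocol 10.1.2.1.2 excludes the test if the patient had already stopped before the Premature EOT visit. Appendix B places the second test at Week 26, "or earlier if the patient terminates study participation before Week 26".

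**Planned checks.** SAP 2.4.4.1 presents washout MI as a sensitivity analysis if retrieved-dropout imputation is used for the primary analysis. Tipping-point analyses cover HbA1c for both doses.

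**The concern.** Estimating the model only from patients who stopped IMP makes sense if their values show what happens after stopping. The SAP does not say this outright, but neither the name nor the restriction has another evident purpose.

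As worded, a patient whose Premature EOT visit is on Day 160, while still taking tablets, and who does not return has that on-drug value filed as Week 26. The patient is then a retrieved dropout and lends the value to others in the arm who stopped months earlier. In a sotagliflozin arm this carries the treatment effect into patients no longer treated.

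Two things follow. The same values count toward the minimum of 5, so they can move an endpoint away from washout MI. And for 2-hour PPG, the first secondary endpoint in the testing sequence, the meal-test rules leave no protocol-compliant off-drug donor, yet retrieved-dropout imputation remains the first-choice method.

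**Working it through.** **1. Planning figures.** SAP 1.3: "Assuming a common standard deviation (SD) of 1.2% and using a 2-sided test at a 0.05" level, 100 per arm. SE = 1.2 × √(2/100) = 0.170.
- 400 mg: the plan states "94% power to detect a treatment difference of 0.6% in mean HbA1c change from Baseline to Week 26". Φ(0.6/0.170 − 1.96) = 94.2%, which agrees.
- 200 mg: stated 84% for 0.5%; Φ(0.5/0.170 − 1.96) = 83.8%, which agrees.

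With 76 patients randomized 1:1 and about 300 randomized 1:1:1 (SAP 1.3), the 400 mg comparison has about 38 + 100 = 138 per arm. Its SE is 1.2 × √(2/138) = 0.144.

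**2. Days at risk.** For Week 26, Days 154 to 181: 28 of 182 days, or 15.4%. For Week 12 SBP, the 70–104 window must be cut at about Day 84, because a patient who stops later was still on IMP when the visit fell due and is not a retrieved dropout.

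**3. Can PPG reach 5 donors?** The documents give no discontinuation rate and expect retrieved dropouts to be few. Assume a rate d spread evenly over 182 days, with every late stopper having an on-drug Premature EOT meal test (an upper-case count). Donors per arm are then Binomial(n, d × 28/182), and the arm probabilities of at least 5 are multiplied.

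| d | Expected donors, n = 138 | Both arms ≥ 5, 400 mg pair | Expected donors, n = 100 | Both arms ≥ 5, 200 mg pair |
|---|---|---|---|---|
| 5% | 1.1 | <0.1% | 0.8 | <0.1% |
| 10% | 2.1 | 0.4% | 1.5 | 0.04% |
| 15% | 3.2 | 4.6% | 2.3 | 0.7% |
| 20% | 4.2 | 18% | 3.1 | 4% |
| 30% | 6.4 | 59% | 4.6 | 24% |

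If only half of late stoppers have an on-drug test, the 400 mg figures at 20% and 30% fall to 0.4% and 4.6%. If all three arms must qualify, as SAP 2.4.4.2 can be read, they are about 3% and 29%.

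**4. HbA1c shift.** Assume 10% of the arm is imputed, 5 donors in all, and an on-drug versus off-drug gap equal to the planned 0.6 points.
- One on-drug donor: 0.10 × (1/5) × 0.6 = 0.012 points in the arm mean.
- All five on drug: 0.10 × 0.6 = 0.06 points, the upper bound.
- A consistent mix: five on-drug donors imply 5/(28/182) = 32.5 stoppers among 138. With 14 missing (10%), 32.5 − 5 − 14 = 13.5 are off-drug donors. The on-drug share is 5/18.5 = 27%, and the shift is 0.10 × 0.27 × 0.6 = 0.016 points.

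**5. Effect on the 5-donor switch for HbA1c.** Assume 10% discontinuation, 138 per arm, and a share r of stoppers returning at Week 26. The donor probability per patient is 0.10r with off-drug values only, and 0.10r + 0.10(1 − r)(28/182) with late EOT values added.
- r = 25%: the chance that both arms reach 5 rises from 7% to 33%; on-drug values are 32% of expected donors.
- r = 50%: from 68% to 82%; 13% of expected donors.

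**The case against.** **The 5-donor rule already protects PPG.** Largely true, as step 3 shows. But the protection comes from scarcity of donors. Nothing in the method recognises that they would be the wrong ones, and the protection weakens as discontinuation rises.

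**A Premature EOT value need not be on drug.** True. Protocol 10.3.3 allows the visit after stopping, and after Week 18 the next on-site visit is Week 26. The counts above are therefore upper-case. For PPG this does not help, since an already-stopped patient should not have the test.

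**HbA1c donors are mixed, and late values are fair stand-ins.** Both stand. Scheduled values take precedence and stoppers are urged to return. Protocol 9.6 says HbA1c reflects the previous 120 days, so a value within 28 days of target is reasonable for that same patient. The difficulty is lending it to early stoppers. A full 0.6-point gap is also an extreme, because other treatments are permitted after stopping, except SGLT2 inhibitors.

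**Sensitivity analyses are planned.** For HbA1c they are, and they answer most of the donor question there. They do not test a re-allocated value: it counts as observed, so washout MI leaves it in place and the tipping-point penalty does not apply. No washout or tipping-point check is specified for PPG, FPG, weight or SBP. The 200 mg sensitivity analyses on selected other endpoints keep the same choice of imputation methods (SAP Appendix D).

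**Conclusion.** The definition has a real gap, with modest expected consequences. The mechanism follows from SAP 2.4.4.1 and 2.5.4 read with Protocol 10.3.3, and applies only to late Premature EOT values with no scheduled value.

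A reader might infer that the PPG result is biased toward sotagliflozin. If stoppers kept no effect and all PPG donors were on drug, the estimate would be overstated by m/(1 − m) for a missing fraction m: 0.10/0.90 = 11%, or 0.15/0.85 = 18%. The documents do not support this as an expectation. At 10% or 15% discontinuation the 400 mg comparison reaches that branch with probability only about 0.4% or 4.6%, and washout MI uses no sotagliflozin donors. The bias is conditional on reaching the branch, which becomes more likely than not only near 30%.

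A reader might also infer a threat to the primary result. A realistic HbA1c shift of 0.01 to 0.02 points, against an SE of about 0.14, does not support that; 0.06 is an upper bound.

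These sizes rest on assumed discontinuation rates, even timing of stopping and the assumed 0.6-point gap. The SAP should still be changed: it permits on-drug donors, lets them influence the choice of method, and specifies no washout check for four of the continuous measures.

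**What to change.** In SAP 2.4.4.1 and 2.4.4.2:
- Define a retrieved dropout as a patient whose endpoint value was measured after the last double-blind dose, and apply the minimum of 5 to those patients only.
- Specify washout MI directly for 2-hour PPG.
- State whether an on-drug Premature EOT value re-allocated under 2.5.4 may stand as that patient's own Week 26 (or Week 12) result.

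A longer gap after the last dose, such as the SAP's 10-day residual period, is optional. That interval was set for safety reporting, is not an HbA1c washout, and would discard some true retrieved dropouts who stopped shortly before Week 26.

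Protocol 9.1.4.2, 10.1.2.1.2, 10.3.3 and Appendix B should be reconciled on which early-stopping patients receive a meal test.

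Apart from that reconciliation, the change is to SAP wording. It leaves fewer donors, so washout MI will be used somewhat more often and estimates may be slightly less favourable to sotagliflozin.

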2.4.4.2 Analyses of secondary efficacy endpoints

For continuous secondary efficacy parameters (see [Section 2.1.3](#)) with missing data at baseline, missing data will be imputed using MI under the missing at random (MAR) assumption. Missing data at baseline will be imputed using regression method that includes randomization stratum of HbA1c (\leq 8.0%, $>$ 8.0%), randomization stratum of SBP (<130 mmHg, \geq 130 mmHg), and baseline value in the imputation model.

Each continuous secondary efficacy endpoint ([Section 2.1.3](#)) will be analyzed using a similar ANCOVA model including the measurements at baseline and endpoint (observed or imputed). The missing data at endpoint will be imputed by the retrieved dropouts if there are at least 5 patients in each study treatment group who discontinued but have the endpoint. Otherwise, the

Statistical Analysis Plan

Version: 3

Lexicon Pharmaceuticals Protocol No. EFC14833

Date of Issue: 21-Nov-2019

Covance Study ID: 000000150524

washout imputation method will be used according to the criterion described in Section 2.4.1. After the imputation, each of the complete datasets will be analyzed by an ANCOVA model.

- To compare sotagliflozin 400 mg versus placebo under the original protocol and Amendment 1, the ANCOVA model will include treatment groups (sotagliflozin 400 mg, placebo), randomization stratum of HbA1c ($\leq 8.0\%$, $> 8.0\%$), randomization stratum of SBP (< 130 mmHg, ≥ 130 mmHg), and country as fixed effects, and the corresponding baseline value as a covariate.
- To compare sotagliflozin 200 mg versus placebo under Amendment 1, the ANCOVA model will include treatment groups (sotagliflozin 200 mg, placebo), randomization stratum of HbA1c ($\leq 8.0\%$, $> 8.0\%$), randomization stratum of SBP (< 130 mmHg, ≥ 130 mmHg), and country as fixed effects, and the corresponding baseline value as a covariate.

For the analysis of SBP in patients with baseline SBP ≥ 130 mmHg, the randomization stratum of SBP will not be included in the ANCOVA model. Results from each complete dataset will be combined using Rubin's formula to provide the adjusted mean change from Baseline to Week 26 (or Week 12 for SBP) for each treatment group, as well as the between-group difference (comparing each sotagliflozin dose group vs its corresponding placebo group) and the 95% CI for the difference.

Sensitivity analyses will be performed to compare sotagliflozin 200 mg and placebo under Amendment 1 for selected other endpoints such as FPG, SBP and HbA1c responders.

For all continuous secondary endpoints, summary statistics at scheduled visits will be provided for each treatment group. The summary will include the number of observations, mean, SD, SE, minimum, median, and maximum. Graphical presentations will also be used to examine trends over time using mean values (\pm SE) and mean changes from baseline (\pm SE) at each of the scheduled visits. In addition, SBP will be summarized descriptively at each visit for those with baseline SBP ≥ 140 mmHg.

The categorical secondary efficacy variables of HbA1c $< 6.5\%$, $< 7\%$ at Week 26 will be analyzed respectively using a Cochran-Mantel-Haenszel (CMH) method stratified by randomization stratum of HbA1c ($\leq 8.0\%$, $> 8.0\%$), and randomization stratum of SBP (< 130 mmHg, ≥ 130 mmHg). The proportion in each treatment group will be provided, as well as the difference between each sotagliflozin group and its corresponding placebo group with the associated 2-sided 95% CI. For HbA1c responders at Week 26 ($< 6.5\%$, $< 7\%$ respectively), all values at Week 26 will be used to determine whether a patient is a responder or not, even if they are measured after IMP discontinuation or rescue medication use. Patients who have no HbA1c measurement at Week 26 will be treated as non-responders. Summary tables and graphs will also be provided by treatment group at scheduled visits.

For between-group comparison, a sensitivity analysis will be performed respectively for HbA1c $< 6.5\%$ responder analysis by excluding patients whose HbA1c values at baseline are $< 6.5\%$, and for HbA1c $< 7\%$ responder analysis by excluding patients whose HbA1c values at baseline are $< 7\%$ using the same CMH test mentioned above. Similarly, by-visit summary may also be provided excluding those patients.

Statistical Analysis Plan

Version: 3

Lexicon Pharmaceuticals Protocol No. EFC14833

Date of Issue: 21-Nov-2019

Covance Study ID: 000000150524

Sensitivity analyses

Tipping point analysis, similar to what is described in [Section 2.4.4.1](#), will be performed to examine the robustness of the treatment effect of sotagliflozin 200 mg on HbA1c, using the same imputation method and ANCOVA model as described above for comparing sotagliflozin 200 mg versus placebo under Amendment 1. The tipping point analysis will be performed only if the secondary endpoint change from baseline to Week 26 in HbA1c for comparing sotagliflozin 200 mg versus placebo is statistically significant at $\alpha = 0.05$ (2-sided).

Similar to what is described in [Section 2.4.4.1](#), the treatment effects (sotagliflozin 200 mg versus placebo under Amendment 1) across the subgroups (see [Section 2.4.4.1](#)) will be estimated for the change from Baseline to Week 26 in HbA1c in the ITT population, and using the same imputation method described above for comparing sotagliflozin 200 mg versus placebo under Amendment 1 in the full analysis dataset. The ANCOVA model will include treatment groups (sotagliflozin 200 mg, placebo), randomization stratum of HbA1c ($\leq 8.0\%$, $> 8.0\%$), randomization stratum of SBP (< 130 mmHg, ≥ 130 mmHg), subgroup factor, treatment-by-subgroup factor, and country as fixed factors and using baseline HbA1c value as a covariate. The adjusted estimates of treatment mean differences (sotagliflozin 200 mg versus placebo) with SE and 95% CIs will be provided as appropriate across the subgroups. A graphical presentation of the results (ie, forest plot) will also be provided.

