The categorical secondary efficacy variables of HbA1c <6.5%, <7% at Week 26 will be analyzed using a Cochran-Mantel-Haenszel method stratified by randomization stratum of HbA1c ( $\leq 8.0\%$ ,  $>8.0\%$ ), and randomization stratum of SBP ( $<130$ ,  $\geq 130$  mmHg). The proportion in each treatment group will be provided, as well as the difference of proportions between each sotagliflozin group and its corresponding placebo group with associated 2-sided 95% CI. For HbA1c responders at Week 26 (<6.5%, <7% respectively), all values at Week 26 will be used to determine whether a patient is a responder or not, even if they are measured after IMP discontinuation or rescue medication use. Patients who have no HbA1c measurement at Week 26 will be treated as non-responders.

For all secondary endpoints, summary statistics at scheduled visits will be provided for each treatment group. The summary will include the number of observations, mean, SD, SE, minimum, median, and maximum. Graphical presentations will also be used to examine trends over time using mean values ( $\pm SE$ ) and mean changes from baseline ( $\pm SE$ ) at each of the scheduled visits (using OC).

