2.4.4.4 Multiplicity issues

To control the family-wise type I error, a fixed-sequence procedure will be applied.

Once the primary variable (change from Baseline to Week 26 in HbA1c) is statistically significant at $\alpha = 0.05$ (2-sided), the following secondary efficacy variables will be tested in the following prioritized order. The testing will stop as soon as an endpoint is found not to be statistically significant at $\alpha=0.05$ (2-sided).

- Comparing sotagliflozin 400 mg versus placebo,
 - Change from Baseline to Week 26 in 2-hour PPG following an MM
 - Change from Baseline to Week 26 in FPG
 - Change from Baseline to Week 26 in body weight
 - Change from Baseline to Week 12 in SBP for patients with baseline SBP ≥ 130 mmHg
 - Change from Baseline to Week 12 in SBP for all patients
 - Proportion of patients with HbA1c $< 7.0\%$ at Week 26
- Comparing sotagliflozin 200 mg versus placebo,
 - Change from Baseline to Week 26 in HbA1c
 - Change from Baseline to Week 26 in 2-hour PPG following an MM
 - Change from Baseline to Week 26 in body weight
 - Change from Baseline to Week 12 in SBP for all patients.

No multiplicity adjustment will be made on efficacy variables other than those mentioned above.

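### The gated HbA1c <7.0% test is a valid stratified CMH test, but it omits continuous baseline HbA1c and so gives up a few points of power just before the 200 mg sequence

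*SAP*

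**What the plan says.** SAP 2.4.4.2 states that the HbA1c <6.5% and <7% responder variables "will be analyzed respectively using a Cochran-Mantel-Haenszel (CMH) method stratified by randomization stratum of HbA1c" (≤8.0%, >8.0%) and also by the SBP randomization stratum (<130, ≥130 mmHg), which makes four strata. Protocol 11.4.2.2 has the same test: the variables "will be analyzed using a Cochran-Mantel-Haenszel method stratified by randomization stratum of HbA1c" and SBP. Both documents count a patient without a Week 26 HbA1c as a non-responder. Both report the difference in proportions with a 95% CI.

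Continuous baseline HbA1c is not in this test. It is a covariate in the HbA1c ANCOVA (SAP 2.4.4.1), and each continuous secondary endpoint is adjusted for its own baseline value (SAP 2.4.4.2). The one extra responder analysis repeats the CMH without patients who were already below the threshold at baseline.

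In SAP 2.4.4.4 and protocol 11.4.2.4, HbA1c <7.0% is the sixth and last 400 mg secondary test. The four 200 mg tests follow. "The testing will stop as soon as an endpoint is found not to be statistically significant at" the two-sided 0.05 level.

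**The concern.** Whether a patient ends below 7.0% depends heavily on the starting value. Screening HbA1c may lie anywhere from 7% to 10% (protocol 7.2.2). In the lower stratum, a patient at 7.1% needs a fall of just over 0.1 points and a patient at 7.9% a fall of just over 0.9, yet the test treats them alike. The information to separate them is already collected and already used in the ANCOVA.

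The place in the sequence gives this weight. If the responder test misses, no 200 mg result can be claimed, including 200 mg HbA1c, which SAP 1.3 powers at 84%. Neither document states a power for the responder test.

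**Working it through.** **Inputs from the documents.** SAP 1.3 gives the level ("using a 2-sided test at a 0.05" level), the spread ("Assuming a common standard deviation (SD) of 1.2"%), and at 100 per arm "94% power to detect a treatment difference of 0.6% in mean HbA1c change from Baseline to Week 26 between sotagliflozin 400 mg and placebo". For 200 mg it states 84% at a true difference of 0.5%. It also gives "76 patients randomized (1;1) under the original protocol, balanced between placebo and sotagliflozin 400 mg", and about 300 more patients at 1:1:1.

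**Assumptions, because the documents give no responder rate, baseline distribution, baseline-change slope or dropout rate.** Underlying HbA1c normal with mean 8.1 and SD 0.9, screening value cut to 7-10%; visit-to-visit SD 0.25; placebo change -0.1 to -0.3; slope of change on baseline 0 to -0.4; SD of change 1.2 or 0.9; 0 to 10% missing, counted as non-responders.

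**Step 1: the plan's own figures.** Power = Φ(δ / (σ√(2/n)) − 1.96).
- n = 100, δ = 0.6, σ = 1.2: 0.6/0.1697 = 3.536, and Φ(1.576) = 94.2% (stated 94%).
- n = 100, δ = 0.5: 0.5/0.1697 = 2.946, and Φ(0.986) = 83.8% (stated 84%).

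Both reproduce.

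**Step 2: the 400 mg comparison.** Per arm, 76/2 + 300/3 = 138. Primary test: 0.6/(1.2√(2/138)) = 0.6/0.1445 = 4.153, and Φ(2.193) = 98.6%.

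**Step 3: rough power of the responder test, no strata.** Power = Φ((p₁ − p₀ − 1.96√(2p̄q̄/n)) / √((p₁q₁ + p₀q₀)/n)). Simulated rates of 20.1% and 35.1% give (0.150 − 1.96 × 0.0538)/0.0531 = 0.839, or 79.9%. Rates of 17.5% and 30.8% give 73.5%.

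**Step 4: CMH against logistic likelihood-ratio tests.** The tests were applied to the same simulated trials: 138 per arm, placebo change -0.2, 4,000 trials per row.

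| Effect, SD | Slope, missing | CMH, 4 strata | Logistic, strata only | Logistic, strata + continuous baseline | Gain over CMH |
|---|---|---|---|---|---|
| 0.6, 1.2 | 0, 10% | 72.9% | 73.4% | 77.0% | 4.1 |
| 0.6, 1.2 | -0.2, 10% | 75.0% | 75.6% | 78.0% | 3.0 |
| 0.6, 1.2 | -0.4, 10% | 79.6% | 80.4% | 82.1% | 2.5 |
| 0.6, 1.2 | 0, none | 80.1% | 80.9% | 83.4% | 3.3 |
| 0.6, 0.9 | -0.2, 10% | 91.2% | 91.8% | 93.5% | 2.3 |
| 0.6, 0.9 | -0.4, 10% | 94.1% | 94.3% | 95.3% | 1.2 |
| 0.4, 0.9 | 0, none | 59.6% | 61.0% | 65.7% | 6.1 |

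The step from CMH to strata-only logistic comes from the form of the test, not the covariate. It is 0.5 to 0.8 points in the four rows at 0.6% and SD 1.2. The last row is the most favorable case found; 1.4 of its 6.1 points come from the form of the test.

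**Step 5: the standardized difference in proportions, baseline-adjusted, against CMH** (8% missing, 3,000 trials per scenario).
- Effect 0.6, SD 1.2: 74.5% to 77.6% with no slope, and 80.5% to 82.0% with slope -0.3. Two further scenarios at the same effect and SD gave 74.9% to 78.7% and 79.6% to 82.1%.
- Effect 0.5, SD 1.2: 59.0% to 61.9%. Effect 0.5, SD 0.9: 79.2% to 82.6%.
- Effect 0.6, SD 0.9: 91.7% to 93.3%.

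**Step 6: size under no effect.** CMH 4.9-5.5%, logistic likelihood-ratio test 5.2-6.0%, standardized difference 5.0-5.3%. The simulation standard error at 4,000 trials is √(0.05 × 0.95/4000) = 0.34 points.

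**Step 7: where the weakness lies.** With no missing data and no slope, the responder CMH stands at 80.1% against 98.6% for the mean-change test, a gap of 18.5 points. Baseline adjustment recovers 3.3 of them.

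**The case against.** The case for leaving the plan alone is substantial. The CMH test is simple, mirrors the randomization, keeps its size and is the same in both documents. The gain is small. In one check at the planned effect and SD, the covariate itself contributed only 2.2 points (no slope) and 1.0 point (slope -0.3). Calibrating each test to its simulated size cut the total likelihood-ratio gain to 1.9 and 1.2 points. In 1.4-1.9% of trials the CMH succeeded and the adjusted test did not. The spread in CMH power from the assumptions, about 73-82% at the same effect and SD, exceeds the gain. All of this stands, and it is why the point is only an optional improvement.

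Two objections concern the form of the adjusted test: a likelihood-ratio p-value can disagree with a CI for a risk difference, and a logistic model changes the effect measure. Both are met by testing the standardized difference itself, which kept essentially all the gain in Step 5.

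A reader might infer more than the documents support:
- That the test adjusts only for the HbA1c stratum. It also stratifies by SBP.
- That baseline HbA1c is ignored. It enters through the screening split and the sensitivity analysis that excludes patients already below the threshold.
- That the CMH choice is what endangers the 200 mg claims. That risk comes mainly from the fixed sequence and from dichotomizing HbA1c. Reaching this test also requires success on the primary and five earlier 400 mg tests, and an adjusted test would still often miss.

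**Conclusion.** The point holds as one of efficiency. The gated responder test omits a strong, already collected predictor. At 138 per arm this costs roughly 1 to 4 points of power in most scenarios. At the planned 0.6% effect and SD of 1.2% the gain ran from 1.5 to 4.1 points, so about 2 to 4. All responder-power figures rest on the assumed baseline distribution, slope, placebo change and missing rate. The direction was the same in every scenario, but the exact size is not established. The documents do not support a finding of bias, inflated type I error or inconsistency between protocol and SAP.

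**What to change.** Before unblinding, amend SAP 2.4.4.2 so that the gated HbA1c <7.0% test is the standardized (marginal) difference in proportions. Fit a logistic model with treatment, both randomization strata and continuous baseline HbA1c. Average each patient's predicted probability under 400 mg and under placebo, and take the difference. Draw both the p-value and the 95% CI from that difference, with a robust standard error (influence-function or delta-method). Keep missing counted as non-response, and report the stratified CMH as supportive.

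The cost is SAP wording and a short program, with no new data. The small downside is a model-based test that departs from the CMH wording in protocol 11.4.2.2, so the change must be recorded as such.
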